15.4 Data Flow

Completed forms (whether electronic or hard copy) will be reviewed by a researcher to ensure completeness and accuracy. Any errors will be crossed out, corrected, and then initialed. After data on digital forms are confirmed to be accurate, researchers will flatten the digital form (to prevent accidental changes to the file) and save it to the participant's digital binder.

- The file name will have descriptive details about what is included in the file (e.g., Resident Assessment, HBC Session Observation / Evaluation Form, etc.)
- In addition, the researcher will end the file name with his/her initials and the date (e.g., dw_2022_01_01)

If any accidental references to the person by name is included on the data form, such references will be redacted and initialed by reviewer. Data from the form will then be entered into the study's master database by the research assistant.

15.5 Retention of Study Documentation

After the study ends, research staff shall maintain participant forms in Hearthstone's HIPAA-compliant database for three years or as indicated by the protocol, federal regulations, and IRB guidance.

16.0 DATA MANAGEMENT

Data Tracking will be conducted in the following way:

- A data tracking spreadsheet will be used. Each row will contain a participant ID and each column will contain a piece of data required for the study (e.g., NPI-NH or DEMQOL). This will allow him to track which data has been and which data will need to be collected (and by when). Once data is collected, he will note the person who collected the data and on what date (e.g., Collected by XX on 7/30/21). It should be noted that separate data tracking spreadsheets will be maintained for each type of participant (PWD, SPs, and Family Members).

Study Form Review will be conducted in the following way:

- After data on digital forms are confirmed to be accurate, researchers will flatten the digital form (to prevent accidental changes to the file) and save it to the participant's digital binder.
 - a. The file name will have descriptive details about what is included in the file (e.g., Resident Assessment, HBC Session Observation / Evaluation Form, etc.)
 - b. In addition, the researcher will end the file name with his/her initials and the date (e.g., dw_2022_01_01)

Data Entry will be conducted in the following way:

- The Research Assistant will enter data directly into SPSS by reviewing the forms. Data will be double-checked for accuracy.

Data Analyses will be conducted in the following way:

- The PI will conduct data analyses using SPSS.

16.1 Quality Control Procedures

All research staff responsible for data collection and management will have received human subjects and, as applicable, good clinical practice training/certification. In terms of training for collection of other measures and adherence to other study protocols, all staff will be trained via standard, in-person training protocols on all measures and will achieve a minimum inter-rater reliability rating of 90% on the primary outcome measures.

16.2 Data and Form Checks

Before data is entered into SPSS, a researcher will check the forms for the following possible issues:

- Missing data or forms
- Out-of-range or erroneous data
- Inconsistent and illogical dates over time
- Data inconsistency across forms and visits
- Not completing all fields of a "completed form" or no reason for missing data is provided

16.3 Site Monitoring

This is a single-site clinical trial since there is one investigational site (Hearthstone) conducting and coordinating the study protocol. As such, the PI and Experimental Team Leader will be jointly responsible for the following monitoring activities:

- Ensuring the rights and safety of participants
- Confirming that the study is conducted in accordance with GCP guidelines
- Ensuring maintenance of required documents
- Verifying adherence to the protocol
- Monitoring the quality of data collected
- Ensuring accurate reporting and documentation of all AEs and unanticipated problems

The study team will meet weekly about the project and each of the above items will be part of the meeting agenda each week. Researchers will voice any concerns or issues related to the above areas during the meeting.

17.0 DATA AND SAFETY MONITORING ACTIVITIES

The roles and responsibilities of the entities monitoring participant safety and study quality are described in the separate Data and Safety and Monitoring Plan. All clinical trials supported by NIA must have a data and safety monitoring plan. This single-site, minimal risk study will be overseen by the PI.

17.1 Reports

The following reports will be produced for this study:

Safety Reports

- Delivered to the IRB as needed and will include a detailed analysis of study progress, AEs, and SAEs.
- Produced by the Experimental Team Leader

Final Report

- Delivered to NIH and IRB no more than 120 days after the completion of the project.
- Produced by the PI and Experimental Team Leader

17.2 Study Completion and Close-Out Procedures

The following study completion and close-out procedures will be used:

- The PI and/or Experimental Team Leader will verify that study procedures have been completed, data have been collected, and study intervention(s) and supplies are returned to the responsible party or prepared for destruction.
- The PI will ensure that all data queries have been completed.
- The PI will ensure that correspondence and study files are accessible for external audits.
- The PI will ensure that the study records are maintained, and any relevant study information reported to the NIA.
- The PI will notify the IRB of the study's completion and store a copy of the notification.
- The PI will prepare a report summarizing the study's conduct.

- The PI will notify participants of the study completion.

17.3 Confidentiality Procedures

The following confidentiality safeguards will be used:

- **Electronic files** – Data identifying participants that are stored electronically will be maintained in a separate file that is saved on a secure, HIPAA-compliant server.
- **Forms** – Forms or pages containing personal identifying information will be separated from other pages of the data forms and be retained in a secure location.
- **Data listings** – Participant name, name code, long-term care chart, record number, and other unique identifiers will not be included in any published data listing.
- **Data distribution** – Data listings that contain participant name, name code, or other identifiers easily associated with a specific participant will not be distributed.
- **Data disposal** – Computer listings that contain participant-identifying information will be disposed of in an appropriate manner.
- **Access** – Participant records will not be accessible to persons outside the site without the express written consent of the participant.
- **Storage** – Study forms and related documents will be retained both during and after study completion and will be stored in a secure location
- **Passwords** – Passwords will be used to provide limitations on general access to computer systems and to the functions that individuals can use. Passwords will be changed on a regular basis.
- **User Training** – Research staff with access to computer systems will be trained in their use and in related security measures. Training will include explanations of how to access the system and a discussion of the need for, and importance of, system security.
- **System Testing** – Prior to the use of a new computer system, and after any modifications, the system will be tested to verify that it performs as expected. Testing will verify that the password-activated access system performs as intended.
- **System Backups** – Backup copies of electronic data will be made on a regular basis.

17.4 Publications

Study results will be made available to the public as soon as possible. Publication of the results of this trial will be governed by the policies and procedures of Hearthstone, NIH guidelines, and standard industry practice. Any presentation, abstract, or manuscript will be made available for review by the sponsor and the NIA prior to submission.

18.0 MOP MAINTENANCE

The MOP will be updated on an as needed basis. When a new revision is made, the following procedure will be followed:

1. The version date on the cover page and footer will be updated with the latest date.
2. A list of key changes will be listed on the cover pages. All changes will be tracked.
3. Previous versions of the MOP will be maintained and saved.

**SAFE at Home: A Service to Provide Social Engagement to
Community-Dwelling Persons With Dementia**

NCT05516147

Statistical Analysis Plan

12/1/23

The SAFE at Home app will be considered successful if persons with dementia exhibit higher levels of positive engagement/affect and lower levels of negative engagement- as measured by the Menorah Park Engagement Scale (MPES)-during the intervention, as compared to known means for standard programming. Multiple observations of participants will be taken during SAFE at Home programming. Then, means will be calculated for each participant for each item (on the MPES) or positive and negative subscale (for the EPWDS). Then, we will conduct a one-sample *t*-test to determine whether there are significant differences between the known means and the means observed during SAFE at Home programming. We will also conduct paired sample *t*-tests to examine whether participants exhibit an improvement in the Dementia-Related Quality of Life Scale (DEMQOL), Geriatric Depression Scale – Short Form (GDS-SF), Neuropsychiatric Inventory – Nursing Home (NPI-NH), and the UCLA Loneliness Scale (ULS).

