1.0 STUDY OVERVIEW

Study Title:

SAFE at Home: A Service to Provide Social Engagement to Community-Dwelling Persons with Dementia

The proposed Phase 1 study will involve initial development and evaluation of a new service called Social Activities For Engagement at Home or SAFE at Home (SaH). SaH will enable PWD to participate in videoconference-based group activities with their peers—i.e., other PWD.

The SAFE at Home app will consist of five main components:

- (1) Get to Know You Portal
- (2) Social Engagement Portal
- (3) Peer-to-Peer Interaction Portal (To Be Developed in Future Phase II Study)
- (4) Self-Study Portal (To Be Developed in Future Phase II Study)
- (5) Staff Training Portal
- (6) Scheduling Portal (To Be Developed in Future Phase II Study)

The study will be conducted by two teams over the course of 12 months. The Development Team (DT) will be responsible for providing the overall vision for the app, as well as website / app development, training creation, and content creation. The Experimental Team (ET) will be tasked with all investigatory work on the project.

Participants

A total of 12 PWD living at home are expected to complete the quasi-experiment. We plan to oversample by 25% to accommodate attrition.

Inclusion / Exclusion Criteria

PWD must be at least 65 years old, speak and read conversational English, and be diagnosed with dementia (any type). PWD will be excluded from the study if they show signs of rapid cognitive decline or physical deterioration over the last six months, as evidenced by medical records.

Baseline Period/Measures

During the 4-week baseline period, the ET will collect the following data. PWD Demographics, medications, diagnoses, and type of dementia will be collected via proxy (family member) interview. The following assessments will be administered directly: The Short Portable Mental Status Questionnaire (SPMSQ-T; Roccaforte et al., 1994), the Dementia Quality of Life Scale (DEMQOL; Smith et al., 2005), the Geriatric Depression Scale-Short Form (GDS-SF; Yesavage & Sheikh, 1986; Yesavage et al., 1983), and the UCLA Loneliness Scale (ULS; Wongpakaran et al, 2020). Researchers will interview family members (FMs) using the Neuropsychiatric Inventory-Nursing Home (NPI-NH; Cummings, 1997; Wood et al., 2001). Using the Menorah Park Engagement Scale (MPES; Camp, Skrajner, & Gorzelle, 2015), researchers will observe PWD engagement and affect via videoconference on four days.

Intervention Period/Measures

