During the 8-week intervention period, PWD will participate in SaH sessions through the Social Engagement Portal. Data on engagement and affect will be collected during SAFE at Home sessions using the MPES. In addition, PWD will answer questions related to satisfaction at the end of each session.

Post-Treatment/Distal Measures:

The DEMQOL, GDS-SF, ULS, and NPI-NH will be re-administered at Post-Intervention, allowing us to investigate possible long-term effects. Changes on these longer-term measures are not expected in this Phase 1 study.

[figure not shown]
This App will be considered successful if (1) At least 85% of PWD agree to take part in 80% of the sessions; (2) mean session length is at least 25 minutes; (3) PWD exhibit higher levels of positive engagement/affect and lower levels of negative engagement during SaH sessions, as compared to baseline (based upon the MPES); and (4) PWD report high satisfaction with the app, defined as 85% being satisfied or very satisfied.

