PWD will participate in SAFE at Home for two months during the Intervention Period of the Study. A variety of data will be collected during and/or after the session.

1. Ease of Use and Satisfaction Measure

After each session, the PWDs will be asked simple questions related to ease of use and

satisfaction (e.g., Did you find the activity easy to use? Did you enjoy the activity? Would you recommend it to others?)

2. Observations of PWD in SAFE AT HOME Sessions w/ MPES

- a. Researchers will observe PWD's engagement and affect during SAFE AT HOME sessions using the MPES (Camp, Skrajner, & Gorzelle, 2015). The MPES is described above. There are six different types of activities, and each activity type will be used at least six times by each SAFE AT HOME group. Each participant will be observed multiple times during the intervention period, so that averages can be calculated for each type of engagement/affect.

Post-Treatment Assessments

The following measures will be collected again at post-treatment:

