9.0 VISIT PROCEDURES

PWD

Screening Procedures

A researcher will confirm that the participant meets the following inclusion/exclusion criteria by interviewing a family member or obtaining medical records for the person:

Inclusion: PWD must be at least 65 years old, speak and read conversational English, and be diagnosed with dementia (any type).

Exclusion: PWD will be excluded from the study if they show signs of rapid cognitive decline or physical deterioration over the last six months, as evidenced by medical records.

Baseline Procedures

Chart Review/Interview with Staff

Researchers will collect the following data from each PWD's chart:

- Demographics (race/ethnicity, education level, marital status, and number of years living in LTC)
- All diagnoses
- Type of dementia
- All meds

Baseline Assessment

A researcher will schedule a time to work with the PWD and conduct a direct interview with him/her to administer the SPMSQ, DEMQOL, GDS-SF, and ULS.

Caregiver Interview

Researchers will interview a caregiver to collect data related to neuropsychiatric symptoms (based upon the NPI-NH) and agitation (based upon the CMAI) exhibited by the PWD. In addition, if needed (i.e., if the PWD was unable to respond to the DEMQOL and/or GDS-SF questions), a researcher will interview the caregiver to administer the proxy version of the DEMQOL and/or GDS-SF.

Observations of Standard Activities

For the Phase I study, we will use a large database of participants engaging in activities as the baseline MPES scores. An independent samples t-test will be conducted to examine differences.

Intervention Period Procedures

PWD will be invited to participate in SAFE at Home sessions via videoconference twice per week for two months. The sessions will be led by a Life Enrichment Professional.

Observations of SAFE AT HOME Sessions

Researchers will observe the PWD taking part in SAFE at Home sessions using the MPES. We will aim to conduct multiple observations for each activity type, so that an average score can be calculated for SAFE AT HOME activity programming. Researchers will follow the standard protocols for using the MPES and be extensively trained on how to properly use these measures.

Treatment Fidelity / Process / Satisfaction Measures

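### The SAP judges success on the MPES alone, whereas the protocol requires three further criteria that the SAP neither mentions nor plans to summarise

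*SAP*

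**What the plan says.** Protocol, section 1.0 (Study Overview), sets out a numbered list of success criteria, with 'and' before the last:

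1. Participation: "This App will be considered successful if (1) At least 85% of PWD agree to take part in 80% of the sessions".
2. Duration: "mean session length is at least 25 minutes".
3. MPES: more positive engagement and affect, and less negative engagement, than at baseline.
4. Satisfaction: "PWD report high satisfaction with the app, defined as 85% being satisfied or very satisfied".

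The SAP is a single paragraph. Its success rule begins "The SAFE at Home app will be considered successful if persons with dementia exhibit higher levels of positive engagement/affect" and continues with lower negative engagement, judged on the MPES against known means for standard programming. It then plans a one-sample t-test on the MPES and paired t-tests on the DEMQOL, GDS-SF, NPI-NH and ULS. Participation, session length and satisfaction do not appear in it.

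On numbers, section 1.0 of the protocol says: "A total of 12 PWD living at home are expected to complete the quasi-experiment. We plan to oversample by 25% to accommodate attrition". Section 9.0 says: "PWD will be invited to participate in SAFE at Home sessions via videoconference twice per week for two months". Section 7.0, which lists six activity types, says: "each activity type will be used at least six times by each SAFE AT HOME group".

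**The concern.** Both documents tell the reader when the app counts as a success, and they give different conditions. The three criteria absent from the SAP are the feasibility and acceptability ones, which matter most in an early evaluation of an app. Meanwhile the SAP plans tests on four longer-term scales on which section 1.0 of the protocol expects no change.

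At stake is the study's headline conclusion. Someone working from the SAP could report success without looking at participation, session length or satisfaction. With about 12 people, missing an 85% threshold by one person is a realistic outcome.

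**Working it through.** **The two rules side by side**

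| Condition | Protocol 1.0 | SAP |
|---|---|---|
| At least 85% of participants take part in 80% of sessions | required | not mentioned |
| Mean session length at least 25 minutes | required | not mentioned |
| Favourable MPES result | required | required |
| 85% satisfied or very satisfied | required | not mentioned |

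Take the MPES condition as the same in both documents. (The comparator and test also differ between them; that is a separate issue and is set aside here.) Every data set that satisfies the protocol then satisfies the SAP, but not the reverse. Disagreement can only take the form of SAP success with protocol failure.

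**Where the line falls with 12 completers (protocol 1.0)**

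- 0.85 × 12 = 10.2, so 11 people are needed.
- 10/12 = 83.3% fails; 11/12 = 91.7% passes.
- A favourable MPES result with 10 of 12 meeting criterion 1 is therefore a success under the SAP and a failure under the protocol.

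**How easily criterion 1 is missed**

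The documents give no expected participation rate, so I assume a true per-person rate p and independent participants. The chance of failing is P(X ≤ 10) = 1 − [12 p¹¹(1 − p) + p¹²].

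| Assumed p | Chance of meeting criterion 1 | Chance of failing |
|---|---|---|
| 0.85 | 0.443 | 55.7% |
| 0.90 | 0.659 | 34.1% |
| 0.95 | 0.882 | 11.8% |

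Criterion 4 has the same 85% bar and criterion 2 is a further hurdle, so on these assumptions the chance of failing the protocol's rule as a whole is at least this large.

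**Secondary: the person base for criterion 1**

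Neither document says whether someone who withdraws counts as not meeting criterion 1 or is left out. The enrolled total is not stated. Oversampling by 25% gives 12 × 1.25 = 15, or 12/0.75 = 16 on another reading. Suppose one person leaves before reaching 80% of sessions:

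- 15 enrolled, 12 meeting it: 12/14 = 85.7% of completers (pass); 12/15 = 80.0% of those enrolled (fail).
- 16 enrolled, 13 meeting it: 13/15 = 86.7% of completers (pass); 13/16 = 81.3% of those enrolled (fail).

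With no drop-outs the two bases agree.

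**Secondary: the session count**

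- Section 9.0, with the 8-week period in section 1.0: 2 × 8 = 16 sessions; 0.80 × 16 = 12.8, so 13.
- Section 7.0: 6 types × 6 uses = at least 36 activity uses per group. If each use were its own session, 0.80 × 36 = 28.8, so 29.
- The two fit together only if sessions average at least 36/16 = 2.25 uses each. Neither document states how many activities a session holds.

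**The case against.** The best defence is that the SAP says 'if', not 'only if', and does not withdraw the protocol's list. Criteria 1, 2 and 4 are simple threshold checks that need no significance test, so the SAP may be meant to cover only the part that does. Satisfaction questions are asked after every session, and a session form is completed for every scheduled session, so these topics have not been dropped from the study. On this view the SAP is incomplete, not contradictory.

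Part of this stands. The gap lies in the success rule and its analysis, and it would be wrong to infer that satisfaction is not being measured. But the SAP does more than list tests: it states a success condition of its own, gives no other, and does not refer back to section 1.0. An analyst who follows it exactly reaches a verdict without the other three criteria.

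Three stronger readings are tempting and are not supported:

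- **Conflict in both directions.** On the success rule alone, it runs one way, as shown above.
- **The 55.7%, 34.1% and 11.8% figures as rates of disagreement.** They are chances that criterion 1 fails under assumed rates. Disagreement also needs a favourable MPES result, and neither document gives a probability for that.
- **16 against 36 sessions as a flat contradiction.** Section 7.0 counts activity uses per group, not sessions, and more than one use per session would reconcile the figures. Section 9.0 largely supplies the session base; what is missing is the link between the two counts.

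It is also fair to say that the protocol never uses the words 'all four'. The joint reading rests on the 'and', which is its ordinary meaning in a numbered list of conditions.

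**Conclusion.** The point holds, and the success rule must be fixed. As written, the SAP can return success where the protocol returns failure; 10 of 12 on participation with a favourable MPES result is enough. This is a wrong decision rule and not merely missing detail, because the two documents attach different conditions to the same conclusion. The example rests on 12 people being assessed and on the list in section 1.0 being joint. The failure probabilities rest on independence and on per-person rates that I have assumed.

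The person base for criterion 1 is a lesser matter. It changes the verdict only if there are drop-outs, and which counts are affected depends on whether 15 or 16 are enrolled. The session count and the SAP's reference to an 'EPWDS', a scale not found in the available protocol text, are matters of reconciliation. A reader might infer that these share the grade of the main point; they do not.

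**What to change.** **Must fix.** Make both documents state one success rule. The preferred route is for the SAP to say that success requires all four criteria in section 1.0 of the protocol, and to report criteria 1, 2 and 4 descriptively against their thresholds. If the sponsor intends the MPES alone to decide, amend section 1.0 instead. Either way the cost is a few sentences and no new test.

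**Suggested.**

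- Fix the person base for criterion 1 before the data are seen. One option is all enrolled participants invited to at least one session, with those who withdraw before reaching 80% counted as not meeting it and completers as a secondary figure. The downside is a less favourable figure when there are drop-outs.
- Reconcile the activity-use count in section 7.0 with the session schedule in section 9.0, so that the 80% has one denominator.
- Define or delete 'EPWDS' in the SAP.

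Before finalising, check that the session form records each person's participation and the session's duration. Check also that the satisfaction questions yield the categories criterion 4 needs: the examples given, such as "Did you enjoy the activity? Would you recommend it to others", are only illustrations and do not show the scale. If either is lacking, a form field would have to be added.

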Orientation. The first two parts of the session will be facilitated one-on-one with the PWD; however, the family member should be nearby to help with any technical issues that the PWD may experience. The final part of the session will be conducted privately with the family member. The purpose of the Cognitive/Communication assessment will be to determine whether the PWD is appropriate for a high cognitive / communication ability group or a middle cognitive / communication ability group. Persons who have low cognitive / communication abilities will have been previously deemed ineligible for SaH (during the Trial Session). The assessment will use Hearthstone's I'm Still Here Skills Inventory (ISH-SI). The ISH-SI has been successfully used for over 10 years to place people in appropriate activity programming for their particular ability level. This 5-10 minute assessment is an adapted version of the MMP/MAS, which was developed and tested in an NIH-funded study (R01AG021508). The ISH-SI assesses cognitive/communication skills by inviting the PWD to participate in three brief activities (Hearthsider Book Club, Sort It Out, and Critic's Corner). These activities determine the extent to which the person can read, look at pictures/videos, and engage in conversation. Participants who score similarly on the ISH-SI will be identified as potential group peers. Further determination as to whether they should be assigned to the same group will be based upon their specific background / interests. **Engagement Professionals** will access this component to learn about PWD who will be taking part in sessions that they will be facilitating. To maintain privacy, they will only have access to information for PWD assigned to their groups. **Members** (PWD and family members) will have access to this portal to confirm/adjust information gathered about his/her interests and background. It should be noted that members do not need to access this portion of the app/website during the Get to Know You Session. In fact, we do not expect members to access this part of the app/website very often (it is possible that they will never do so). However, since information about the PWD will be saved here (in a way that is HIPAA-compliant), it is important for us to provide access to this information, so that we are transparent about the data we collect.

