(2) Social Engagement Portal (For All User Types) [Phases 1 and 2] This will allow for Engagement Professional-led social engagement of multiple Members simultaneously and is the central component of the product. **Members** (PWD, likely with the help of a family member) will access this portion of the app to participate in social engagement sessions. A list of upcoming sessions will be shown when accessing this portion of the website. To join a session, they will simply click "Start Now" to be connected via videoconference to an Engagement Professional and up to five other PWD. Members will be able to go to the Social Engagement Portal to start each session or they will be able to click on a link included in the reminder email that will be sent. **Engagement Professionals** will facilitate a session by interacting with participants via the webcam but will also share their screen with participants to show the activity content. As mentioned earlier, activities that have been shown to be effective in prior research will be used. Everything an Engagement Professional needs to facilitate a session will be included in the Social Engagement Portal, including access to the activities. **Engagement Coaches** will also have access to the Social Engagement Portal. They will drop in unannounced to audit sessions, but not appear on video. The goal is for the Engagement Coach to make certain that high quality sessions are being offered to members and that fidelity to the procedures is being maintained in order to ensure a high quality intervention. Please note: [name] [PI] conducted six proof of concept activity sessions with 18 PWD via videoconference to determine whether conducting sessions using this methodology would be successful. In all cases, PWD were able to engage in the activities and generally seemed to enjoy participating. In a few cases, PWD spoke very quietly, which made it hard for [name] to hear their responses. But this was due to the fact that they were too far away from their tablet. So, we will instruct family members to place the device very close to their loved one for sessions, and to encourage PWD use headsets with mics, to avoid such issues in the future.

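### Does the MPES t-test need a clustering adjustment because participants are rated in shared small groups?

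*SAP*

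**What the plan says.** Protocol section 6.0 forms groups by ability: "Participants who score similarly on the ISH-SI will be identified as potential group peers". Background and interests then refine the choice. Engagement Professionals are tied to groups, since "they will only have access to information for PWD assigned to their groups". In a session each member is "to be connected via videoconference to an Engagement Professional and up to five other PWD", so a group has at most six members.

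Delivery is also by group. Section 7.0 states: "There are six different types of activities, and each activity type will be used at least six times by each SAFE AT HOME group". MPES ratings are made in these sessions: "Each participant will be observed multiple times during the intervention period" (section 7.0) and "We will aim to conduct multiple observations for each activity type" (section 9.0). The schedule in section 9.0 is: "PWD will be invited to participate in SAFE at Home sessions via videoconference twice per week for two months".

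For analysis, the SAP averages within person ("Then, means will be calculated for each participant for each item (on the MPES") and applies a one-sample t-test against known means. Protocol sections 7.0 and 9.0 name an independent-samples t-test against a database. Neither has a group, session or facilitator term. Section 1.0 expects 12 completers.

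**The concern.** Both tests treat the participants' means as independent. Averaging within a person deals with repeated ratings of that person. It does not deal with likeness between people who share sessions, peers and a facilitator. Some likeness is plausible, because the MPES defines constructive and passive engagement by reference to the target activity, which everyone in a session shares.

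With positive correlation, the variance of the overall mean exceeds what the t-test assumes, so p-values are too small and the implied interval too narrow. The MPES comparison is the SAP's only success statement and one of four success criteria in Protocol section 1.0. A reader could take a significant result as firmer than it is.

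**Working it through.** **Inputs from the documents.** N = 12 completers (Protocol 1.0). Maximum group size is 6 (Protocol 6.0, Social Engagement Portal). Two sessions a week over the 8-week intervention period (Protocol 9.0 and 1.0) give 2 × 8 = 16 sessions.

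**Assumptions.** The level is two-sided 5%. Layouts are two groups of six, three of four, or four of three; the lower limit of three is stated only for the Phase 2 Scheduling Portal. The ICC of participant means is set at 0 to 0.20. The documents give no power calculation or ICC, so there is no planned figure to reproduce.

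**Formulas.** With group size m and ICC ρ:

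- variance of the mean = (σ²/N)[1 + (m − 1)ρ]
- expected sample variance = σ²[1 − (m − 1)ρ/(N − 1)]
- true over assumed standard error = √{[1 + (m − 1)ρ] / [1 − (m − 1)ρ/(N − 1)]}

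For m = 6 and ρ = 0.10: √(1.5 / 0.9545) = 1.254. For m = 3: √(1.2 / 0.9818) = 1.106.

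**Type I error of the planned one-sample t-test** (11 df, critical value 2.201; simulated, good to about 0.1 percentage point):

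| ICC | 2 groups of 6 | 3 groups of 4 | 4 groups of 3 |
|---|---|---|---|
| 0 | 5.0% | 5.0% | 5.0% |
| 0.05 | 7.7% | 6.6% | 6.1% |
| 0.10 | 10.8% | 8.4% | 7.2% |
| 0.20 | 16.9% | 12.1% | 9.6% |

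A negative ICC makes the test conservative: at −0.05 the rates are 2.6%, 3.5% and 4.0%.

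**Which ICC is plausible?** Suppose session explains a share s and person a share p of the variance of a single rating, and all members are rated in the same k sessions. Then

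ICC of means = (s/k) / [p + s/k + (1 − s − p)/k].

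Take s from 0.10 to 0.30 and p from 0.30 to 0.50 (assumed). At k = 16:

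- low end (s = 0.10, p = 0.50): 0.00625 / (0.50 + 0.00625 + 0.025) = 0.012
- high end (s = 0.30, p = 0.30): 0.01875 / (0.30 + 0.01875 + 0.025) = 0.055

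| Rated sessions | ICC of means | Error, 2 groups of 6 | Error, 4 groups of 3 |
|---|---|---|---|
| 4 | 0.040–0.158 | 7.1%–14.3% | 5.9%–8.6% |
| 16 | 0.012–0.055 | 5.7%–8.1% | 5.2%–6.2% |
| 36 | 0.005–0.026 | 5.3%–6.4% | 5.2%–5.6% |

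The 36 row reads six activity types used six times each (6 × 6) as separately rated sessions. None of these cases reaches an ICC of 0.20.

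**What would a remedy buy?** A t-test on group means holds 5% but has 1, 2 or 3 df for two, three or four groups. With no clustering at all, its 95% half-width is 12.71/√12 = 3.67 SD, 4.30/√12 = 1.24 SD or 3.18/√12 = 0.92 SD, against 2.201/√12 = 0.635 SD for the planned test. Widening the planned interval by the factor above restores about 5% if the assumed ICC is right. If the data are in fact independent, the widened interval errs only 1.9% to 3.3% of the time at ICC 0.10, and 0.75% to 2.3% at ICC 0.20.

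**The case for a change.** The strongest case for a change is that the design makes correlation likely and a remedy costs one paragraph and one table. The number of rated sessions is not fixed, and persistent peer or facilitator effects do not average out over sessions, so the 16-session figures may be too low. A prespecified table over several ICCs would show how far the MPES result leans on independence, without touching the planned test.

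The premise stands, and so does the point about persistent effects, whose size cannot be judged from the documents. The remedy is where the case fails. The table would leave the success criterion unchanged and carry no decision rule. Its ICC values would be chosen without any basis in the documents, and non-negative values can only widen the interval. It would miss a facilitator shared by several groups, one of the suspected sources of correlation. It would also adjust a confidence interval that the SAP does not mention. Once group sizes are reported, any reader can apply the factor.

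**Conclusion.** The independence assumption is unchecked, but it is not shown to be wrong, and no change to the plan follows. The likely inflation from session effects alone is modest: about 5.2% to 8.1% instead of 5%, given 12 completers, groups of three to six, about 16 rated sessions and the variance shares assumed above. It would be larger with few rated sessions or lasting group effects, and absent at an ICC of zero. Sorting by ability does not by itself invalidate the test.

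The stakes are limited as well. Criterion (3) in Protocol section 1.0 and the SAP's success sentence are both directional. The SAP then tests for significance but sets no p-value threshold for success. For a 12-person Phase 1 study, a participant-level t-test is a fair trade-off when the group-level alternative has 1 to 3 degrees of freedom.

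What remains is reporting detail that an analyst would normally supply: the number and size of groups, rated sessions per participant, group means shown descriptively, and independence named as a limitation beside the MPES p-values. Two neighbouring questions are separate and add no weight here: the one-sample versus independent-samples wording, and how at least 36 activity uses fit into about 16 sessions (36/16 = 2.25 per session).
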